**Table 5: Schedule of Events (Continued)**

Visit Number	Screening	Double-blind, placebo-controlled phase										Active treatment phase				Observational follow-up a
	1	2 b (Baseline)	3	4	5	6	7	8	9	10	11	12	13	14/ET	15	
Week	-4 to 0	0	2	4	6	8	10	12	14	16	20	24	28	32	4 weeks after last dose	
Day	-28 to 0	1	15	29	43	57	71	85	99	113	141	169	197	225	-	
Allowance (days)	-	-	±2	±2	±2	±2	±2	±2	±2	±2	±4	±4	±4	±4	±7	
Weight j	X	X	X	X	X	X	X	X	X	X	X	X	X	X	X	
Complete physical examination j	X	-	-	-	-	-	-	-	-	X	-	-	-	X	-	
Limited physical examination k	-	X	X	X	X	X	X	X	X	-	X	X	X	-	X	
Hepatitis B and C l	X	-	-	-	-	-	-	-	-	-	-	-	-	-	-	
Clinical laboratory evaluations (Hematology/Chemistry) m	X	X	-	-	-	X	-	-	-	X	-	X	-	X	X	
Clinical laboratory evaluations (Immunology/Inflammation) m	-	X	-	-	-	X	-	-	-	X	-	X	-	X	X	
Clinical laboratory evaluations (Urinalysis) m	X	-	-	-	-	-	-	-	-	-	-	-	-	-	-	
EFFICACY ASSESSMENT(S)																
PPPASI n	X	X	X	X	X	X	X	X	X	X	X	X	X	X	X	
Modified PPPASI o	-	X	X	X	X	X	X	X	X	X	X	X	X	X	X	
PPSI p	-	X	X	X	X	X	X	X	X	X	X	X	X	X	X	
PGA for palms and soles q	-	X	X	X	X	X	X	X	X	X	X	X	X	X	X	
SUBJECT REPORTED OUTCOMES / QUALITY OF LIFE																
Subject's assessment for PPP signs/findings (using PPSI scale) r	-	X	X	X	X	X	X	X	X	-	X	-	X	-	X	
Subject's VAS assessment for PPP symptoms for hands and feet s	-	X	X	X	X	X	-	X	-	X	-	X	-	X	X	
DLQI t	-	X	-	-	-	X	-	-	-	X	-	X	-	X	-	
EQ-5D t	-	X	-	-	-	X	-	-	-	X	-	X	-	X	-	

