**Table 2: Study Efficacy Endpoints (Continued)**

Endpoint	Name	Description	Timeframe
Exploratory (cont.)	SRO: Subject's assessment for each sign/finding of PPP (Erythema, Pustules/Vesicle and Desquamation/Scale) PPSI scale is used for assessment. Details are shown in Appendix G .	Change from baseline.	By visit in double blind, placebo-controlled phase, Week 24 and 32 in active treatment phase and follow-up (except for baseline)
	SRO: DLQI See Appendix H .	Change from baseline.	Week 8, 16, 24 and 32
	SRO: EQ-5D See Appendix I about EQ-5D	Change from baseline of the utility index and VAS score.	Week 8, 16, 24 and 32
	PPPASI: PPPASI-50	Proportion of subjects who achieve a PPPASI- 50 at each visit.	By visit in active treatment phase
	PPPASI: PPPASI-75	Proportion of subjects who achieve a PPPASI- 75 at each visit.	By visit in active treatment phase
	PPPASI total score	Percent change from baseline.	By visit in active treatment phase
	PPSI total score	Percent change from baseline.	By visit in active treatment phase
	PGA score for palms and soles	Change from baseline.	By visit in active treatment phase
		Proportion of subjects who achieve a PGA score of cleared (0) or minimal (1)	By visit in active treatment phase
		Proportion of subjects who achieve a PGA score of cleared (0) or minimal (1) and have at least a 2-grade improvement	By visit in active treatment phase
Exploratory (cont.)	SRO: Subject's VAS assessment for PPP symptoms	Change from baseline.	Week 24 and 32 in active treatment phase

[figure not shown]
AUC = Area under the curve; DLQI = Dermatology Life Quality Index; EQ-5D = EuroQol 5 Dimension; modified PPPASI-50 = defined as  $\geq 50\%$  improvement of modified PPPASI total score from baseline; modified PPPASI-75 = defined as  $\geq 75\%$  improvement of modified PPPASI total score from baseline; PGA = Physician's Global Assessment; PPP = Palmoplantar pustulosis; PPPASI = Palmo-Plantar Pustulosis Area and Severity Index; PPPASI-

50 = defined as  $\geq 50\%$  improvement in PPPASI total score from baseline; PPPASI-75 = defined as  $\geq 75\%$  improvement in PPPASI total score from baseline; PPSI = Palmo-Plantar Severity Index; SRO: Subject's Reported Outcome; VAS = Visual Analogue Scale.

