### 6.2.1. End of Treatment

An end of treatment (EOT) evaluation will be performed on Visit 14 (Week 32) or for subjects who are withdrawn from treatment for any reason as soon as possible after the decision to permanently discontinue treatment has been made.

For Visit 15 (4 Weeks After Last Dose), an administrative window of  $\pm$  7 days is permitted.

The following evaluations will be performed as specified in the Table of Events ([Table 5](#)):

- Status of smoking
- Concomitant medications and procedures evaluation
- AE/SAE evaluation (monitored through 28 days after the last dose of IP)
- Psychiatric evaluation
- Pregnancy test for FCBP
  - Urine dipstick pregnancy test will be performed.
- Vital signs
- Weight
- Complete physical examination (source documented only)
- Clinical laboratory evaluations
  - Hematology/Chemistry
  - Immunology/Inflammation
- Efficacy assessment (see [Section 6.4](#))
  - PPPASI, PPSI, PGA and modified PPPASI
- Subject reported outcomes or quality of life questionnaires (see [Section 6.7](#))
  - Subject's VAS assessment for PPP symptom, Subject's assessment for PPP signs/findings,
  - DLQI, EQ-5D

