**Table 3: Exploratory Efficacy Endpoints**

Assessment	Description	Timeframe
PPPASI: Three sub scores (Erythema, Pustules/Vesicle, Desquamation/Scale)	Change from baseline of individual sub scores	By visit in double blind, placebo-controlled phase, active treatment phase and follow-up
Modified PPPASI: modified PPPASI-50	Achieving a modified PPPASI-50 response	By visit in double blind, placebo-controlled phase, active treatment phase and follow-up
Modified PPPASI: modified PPPASI-75	Achieving a modified PPPASI-75 response	By visit in double blind, placebo-controlled phase, active treatment phase and follow-up
Modified PPPASI total score	AUC	Week 0-16
Modified PPPASI: Two sub scores (Pustules, Vesicle)	Percent change from baseline	By visit in double blind, placebo-controlled phase, active treatment phase and follow-up
	Change from baseline of individual sub scores	By visit in double blind, placebo-controlled phase, active treatment phase and follow-up
SRO: Subject's assessment for each sign/finding of PPP (Erythema, Pustules/Vesicle and Desquamation/Scale) (PPSI scale is used for assessment)	Change from baseline	By visit in double blind, placebo-controlled phase, active treatment phase and follow-up
SRO: DLQI	Change from baseline	Week 8, 16, 24 and 32
SRO: EQ-5D	Change from baseline of the utility index and VAS score	Week 8, 16, 24 and 32
PPPASI: PPPASI-50	Achieving a PPPASI-50 response	By visit in active treatment phase
PPPASI: PPPASI-75	Achieving a PPPASI-75 response	By visit in active treatment phase
PPPASI total score	Percent change from baseline	By visit in active treatment phase
PPSI total score	Percent change from baseline	By visit in active treatment phase
PGA score for palms and soles	Change from baseline	By visit in active treatment phase
	Achieving a PGA score of cleared (0) or minimal (1)	By visit in active treatment phase
	Achieving a PGA score of cleared (0) or minimal (1) with at least a 2-grade improvement	By visit in active treatment phase

CC-10004 (Apremilast)

Statistical Analysis Plan. Protocol CC-10004-PPP-001

Assessment	Description	Timeframe
SRO: Subject's VAS assessment for PPP symptoms	Change from baseline	By visit in active treatment phase

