5.4. Time points

Time points in all analyses are based on the remapped visits/study weeks using the following visit mapping algorithm, which may not be the same as the visits/study weeks as recorded in the database.

All visit-based data, except for those with the recorded visit being a follow-up visit, will be assigned to analysis visits based on study day (the date of assessment/collection relative to the reference date) and the defined analysis visit windows as below, rather than the recorded visit. The only exception is that the data with a recorded visit being a follow-up visit will be assigned to the analysis visit corresponding to the follow-up visit.

Table 4 Table for Visit Mapping for by Time Point Analysis

Analysis Visit	Target Day	Analysis Window
Week 0 (Visit 2: Baseline)	1	≤ 1
Placebo-controlled Period		
Week 2 (Visit 3)	15	2 – 21
Week 4 (Visit 4)	29	22 – 35
Week 6 (Visit 5)	43	36 – 49
Week 8 (Visit 6)	57	50 – 63
Week 10 (Visit 7)	71	64 – 77
Week 12 (Visit 8)	85	78 – 91
Week 14 (Visit 9)	99	92 – 105
Week 16 (Visit 10)	113	106 – End of the Period
Active Treatment Period		
Week 20 (Visit 11)	141	One day after the first apremilast dosing day on Visit 10* – 154
Week 24 (Visit 12)	169	155 – 182
Week 28 (Visit 13)	197	183 – 210
Week 32 (Visit 14)	225	211 – End of the Period

* The first apremilast dosing day on Visit 10 shall be used for adverse event data

Time points in the analyses or summaries of efficacy data over time include the scheduled study weeks per protocol, the end of a study phase, and the post-treatment observational follow-up phase when applicable. It is possible that multiple assessment values will fall into the same visit window. The following rule may be used to select the unique value for that analysis visit:

Among all assessments in the same visit window for the analysis visit, select the value with the assessment date closest to the target day of the analysis visit;

1. If the relative days from 2 assessments are equally close to, but on different sides of the target day, then the latter assessment will be used for that analysis visit;
2. If multiple assessments are available on the same relative day, then the highest (worst) value of these assessments will be used for that relative day.

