10.3.2. Continuous Variables

The continuous variables for secondary and exploratory endpoints in placebo-controlled phase include the following:

- AUC for PPPASI total score from baseline through Week 16
- PPPASI total score change from baseline at Week 16
- AUC for PPSI total score from baseline through Week 16
- PPSI total score change from baseline at Week 16
- AUC for modified PPPASI total score from baseline through Week 16
- Modified PPPASI total score change from baseline at Week 16
- Subject's assessment for PPP sign/finding (PPSI total score) at Week 16

The analysis of covariance (ANCOVA) model with treatment and stratification factor as the fixed effects, the associated baseline value as the covariate and multiple imputation (MI) method to impute the missing data will be applied. Within-group least-squares (LS) means, the associated standard error (SE), and treatment differences in LS means, the associated SE, and associated 2-sided 95% CIs and 2-sided p-values (nominal) will be derived from the model.

Missing value of at Week 16 will be imputed using the MI method ([SAS Institute Inc. 2015](#)) except for AUC. The SAS procedure MI will be used to impute missing scores to create M=100 complete data sets. The missing data patterns will be checked by treatment at baseline, and Week 2, 4, 6, 8, 10, 12, 14, and 16. If there are non-monotone missing patterns, following two separate imputation procedures will be used to complete the imputation process.

1. In the first step, the Markov Chain Monte Carlo (MCMC) method will be used to impute missing scores by treatment to create M=100 imputed data sets with monotone missing patterns. The minimum and maximum values for imputation will correspond to the lowest and the highest scores. The seed will be set at random, a single chain will be used to produce imputations. In case there are convergence issues, a simple model will be used to impute the

CC-10004 (Apremilast)

Statistical Analysis Plan. Protocol CC-10004-PPP-001

missing scores by treatment, with further simplification by dropping both treatment and stratification factor in imputation model if necessary.

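### The Schedule of Events leaves the subject's PPP signs/findings assessment unmarked at Weeks 16, 24 and 32, against Protocol Table 2, Section 6.2.1 and the SAP's Week 16 analysis of this exploratory endpoint

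*Protocol*

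**What the plan says.** Five places bear on when the subject rates erythema, pustules/vesicles and desquamation on the PPSI scale.

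- **Protocol Table 5.** The row "Subject's assessment for PPP signs/findings (using PPSI scale" has 15 cells under 15 visit columns. It is blank (a dash) at screening, X at Visits 2 to 9 (Weeks 0 to 14), then dash, X, dash, X, dash at Visits 10 to 14 (Weeks 16, 20, 24, 28, 32), and X at follow-up.
- **Protocol Table 2** lists the change from baseline as an exploratory endpoint with this timeframe: "By visit in double blind, placebo-controlled phase, Week 24 and 32 in active treatment phase and follow-up (except for baseline".
- **Protocol Section 6.2.1** states: "An end of treatment (EOT) evaluation will be performed on Visit 14 (Week 32", or as soon as possible after early withdrawal from treatment. Its list for that visit includes "Subject's VAS assessment for PPP symptom, Subject's assessment for PPP signs/findings".
- **SAP Table 3** also classes the endpoint as exploratory and gives the timeframe as "By visit in double blind, placebo-controlled phase, active treatment phase and follow-up".
- **SAP 10.3.2** includes among its ANCOVA endpoints "Subject's assessment for PPP sign/finding (PPSI total score) at Week 16", with missing values multiply imputed. It adds: "The missing data patterns will be checked by treatment at baseline, and Week 2, 4, 6, 8, 10, 12, 14, and 16".

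Table 5 governs collection. Section 6.2 ties the frequency of assessments to it, Section 6.2.1 also refers to it, Section 6.7.2 gives no visit list of its own, and Section 6 rules out waivers.

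**The concern.** Week 16 is the end of the placebo-controlled comparison and the time of the primary analysis. A site working from Table 5 would not hand out this questionnaire there, yet the SAP fits a model to the result. The item asks for the worst status since the previous visit, so a skipped rating cannot be reconstructed later. The Week 20 rating cannot replace it, because by then placebo subjects have switched to apremilast.

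At stake is the between-arm comparison of subject-rated signs at Week 16, together with the planned Week 24 summary and possibly the Week 32 summary.

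**Working it through.** The plan gives no figure for this endpoint to reproduce. Its sample size of 86 rests on PPPASI-50 and plays no part here. The check sets the sources side by side and then passes the scheduled days through the SAP's analysis windows.

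**Step 1. Compare the schedules from Week 16 on.**

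| Visit (week) | Table 5 row | Protocol Table 2 | SAP Table 3, read literally |
|---|---|---|---|
| 10 (16) | – | required | included; also named in SAP 10.3.2 |
| 11 (20) | X | not listed | included |
| 12 (24) | – | required | included |
| 13 (28) | X | not listed | included |
| 14 (32) | – | required; also in Section 6.2.1 | included |
| 15 (follow-up) | X | required | included |

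From screening to Week 14 and at follow-up, Table 5 and Protocol Table 2 agree. They disagree at all five visits from Week 16 to Week 32: three required visits are unmarked and two unlisted visits are marked.

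**Step 2. Can a neighbouring scheduled visit supply a Week 16 or Week 24 value?** Target days and tolerances come from Table 5, and windows from SAP Table 4.

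- Week 14 visit: 99 ± 2 = Days 97 to 101. The Week 14 window is Days 92 to 105, and the Week 16 window is "106 – End of the Period". The visit stays in Week 14.
- Week 20 visit: 141 ± 4 = Days 137 to 145. The Week 20 window runs to Day 154 and the Week 24 window is Days 155 to 182. The visit stays in Week 20.
- Week 28 visit: 197 ± 4 = Days 193 to 201. The Week 28 window is Days 183 to 210. The visit stays in Week 28.
- Records labelled follow-up are always mapped to follow-up.

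Under the Table 5 row, scheduled values in the Week 16 window number 0, and in the Week 24 window 0. The only route to a Week 16 value is an end-of-treatment assessment under Section 6.2.1 in a subject who withdraws on or after Day 106 of the double-blind phase. Such subjects are a selected group.

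**Step 3. What imputation could do.** SAP 10.3.2 uses MCMC by treatment to reach a monotone pattern, then predictive mean matching with K = 2 closest observations. Matching draws from observed values at the visit being imputed. With no scheduled Week 16 observations in either arm, there is no Week 16 distribution to fit and there are no donors.

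**Step 4. What kind of error the row looks like.** From Week 16 the row reads – X – X – X, and Table 2 implies X – X – X X. Moving the printed cells one column to the right from Week 16 reproduces Table 2 for Weeks 16 to 32, and only the follow-up cell then differs. The VAS row directly below also has 15 cells and agrees with Protocol Table 2 over Weeks 2 to 32. This points to a displacement of one column over Visits 10 to 14.

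**The case against.** The strongest objection is that the row may be a table-reading artefact. The evidence is one row of a table extracted from PDF, and several rows on the first page of Table 5 come out with 16 cells for 15 visits. Losing one X and gaining one dash would turn the row implied by Table 2 into the one seen. This cannot be excluded and it limits confidence. It does not dispose of the point. The surplus cells on the first page trail at the end and leave the first 15 positions correct. Every assessment row on the page in question has 15 cells. A single lost cell is not enough either, because the printed row also needs an extra dash before follow-up.

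It is also fair to say that Protocol Table 2, Section 6.2.1 and SAP 10.3.2 all presuppose collection and that the case report form is not available here. So a reader might infer that the trial will have no data at Weeks 16, 24 and 32, but the documents do not show that. They show a contradiction whose consequence depends on which page sites followed. At Week 32 the inference is weakest, since Section 6.2.1 names the assessment at that visit.

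A reader might also infer that the Week 20 and 28 ratings serve no endpoint and can be dropped. That holds only under Protocol Table 2. SAP Table 3, read literally, covers both weeks. Its phrase may be shorthand for whichever visits are scheduled, since it uses similar wording for the VAS, which Table 5 schedules only at Weeks 24 and 32 in the active phase. The documents do not settle this, and deleting the two marks outright could replace one mismatch with another.

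Protocol Table 2 does not invite the same shorthand reading for Week 16. It spells out reduced visit lists where it wants them, as it does for the VAS.

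**Conclusion.** The contradiction holds as a conflict between documents. Table 5, as transcribed, differs from Protocol Table 2 at five of 15 visits and leaves the SAP's Week 16 analysis of this assessment without a scheduled observation. If the row is followed, none of the roughly 86 subjects has a scheduled value in the Week 16 or Week 24 window, and the last scheduled double-blind value is Week 14. Week 32 should be described only as a conflict between Table 5 and Section 6.2.1.

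This assumes that the row is printed in the protocol as it was extracted and that sites work from Table 5.

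The reach is limited. The endpoint is exploratory in both documents and its p-value is nominal. PPPASI, modified PPPASI, PPSI and PGA are marked at every visit from Week 0, so it would be wrong to infer any effect on the primary endpoint, the investigator-assessed endpoints or the sample size. The correction is still worth making because Week 16 is the time of the controlled comparison and a missed rating is not recoverable.

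**What to change.** 1. Check the row against the original page of Table 5.
2. If it is printed as transcribed, mark X at Visits 10, 12 and 14, which agrees with Protocol Table 2, Section 6.2.1 and SAP 10.3.2.
3. Decide whether Weeks 20 and 28 are to be analysed, state the same timeframe in Protocol Table 2 and SAP Table 3, and keep or remove the X at Visits 11 and 13 to match.
4. If sites have already followed the row as printed, amend SAP 10.3.2 before unblinding so that this endpoint is analysed at Week 14, and end its imputation visit list at Week 14.

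The cost is one table row and one SAP timeframe. The burden on subjects is a three-item questionnaire at Weeks 16, 24 and 32, when the VAS, DLQI and EQ-5D are already being completed.

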**Table 5: Schedule of Events (Continued)**

Visit Number	Screening	Double-blind, placebo-controlled phase										Active treatment phase			Observational follow-up a
	1	2 b (Baseline)	3	4	5	6	7	8	9	10	11	12	13	14/ET	15
Week	-4 to 0	0	2	4	6	8	10	12	14	16	20	24	28	32	4 weeks after last dose
Day	-28 to 0	1	15	29	43	57	71	85	99	113	141	169	197	225	-
Allowance (days)	-	-	±2	±2	±2	±2	±2	±2	±2	±2	±4	±4	±4	±4	±7
INVESTIGATIONAL PRODUCTS (IP)															
Randomization (IRT)	-	X	-	-	-	-	-	-	-	-	-	-	-	-	-
Dispense IP	-	X	-	X	-	X	-	X	-	X	X	X	X	-	-
Return and count IP tablets (IP accountability)	-	-	-	X	-	X	-	X	-	X	X	X	X	X	-

Abbreviation: AE = Adverse event; DLQI = The Dermatology Life Quality Index; EQ-5D = Euro QOL 5 Dimension; ET = Early Termination; FCBP = Females of childbearing potential; IP = Investigational Product; IRT = Interactive Response Technology; PAO = Pustulotic arthro-osteitis; PGA = Physician's Global Assessment; PPP = Palmoplantar pustulosis; PPPASI = Palmo-Plantar Pustulosis Area and Severity Index; PPSI = Palmo-Plantar Severity Index; QOL = Quality of Life; RNA = Ribonucleic Acid; VAS = Visual Analogue Scale.

a Subjects who discontinue treatment with IP or withdraw during the treatment phase will be also asked to enter the 4-week observational follow-up phase after ET assessment.

b Visit 2 is Day 1 (Week 0) and the baseline for all Efficacy Assessments. All assessments should be conducted prior to the first administration of IP.

c Written informed consent will be obtained by the Principal Investigator or designee prior to performing any study assessments.

d A complete medical history must be taken and must include a query about whether a subject has known active current or history of recurrent infections.

e Disease history will capture the following information: specific information regarding diagnosis, presence or absence of focal infection, ie, periapical pathosis, periodontitis, angina and sinusitis, Presence or absence of regular dental examination and presence or absence of PAO.

f Dental examination must be conducted by a dentist at Screening and obtain data if there is any dental focal infection (eg, chronic periapical periodontitis, chronic marginal periodontitis) or not, and to evaluate the necessity of treatment (any endodontic treatment for periapical pathosis [eg, infected root canal treatment, tooth extraction], and periodontal surgery for moderate to severe periodontitis). Investigators should evaluate whether a treatment for focal infection is preferred to study enrolment.

g Including smoking history (years/amount) and current status (yes/no and average packs/day).

h Inadequate response to PPP by the treatment with topical steroid and/or topical vitamin D3 derivative preparations should be confirmed.

i At any time when suicidal thoughts or a suicide attempt is identified, evaluate the need for referral to a psychiatrist and other actions, including discontinuation, as required in [Section 6.5.2](#).

j See [Section 6.5](#).

k A limited physical exam may be performed to evaluate an AE, or for any reason, at the discretion of the Investigator.

 See Section 6.5.6

m Each panel of clinical laboratory evaluations is described in Section 6.5.10. Unscheduled clinical laboratory evaluation is acceptable (eg, to follow AEs)

n See [Appendix B](#).

o See [Appendix F](#).

[figure not shown]
p See [Appendix C](#).

q See [Appendix D](#).

r Worst status between the visit in which an assessment is scheduled and the previous visit should be recorded. Indicated assessments should be performed before any tests, procedures, or other consultations (PPPASI, modified PPPASI, PPSI, and PGA for palms and soles) for that visit. See [Appendix G](#).

s Worst status between the visit in which an assessment is scheduled and the previous visit should be recorded. PPP-related symptoms should be included in these assessments. Indicated assessments should be performed before any tests, procedures, or other consultations (PPPASI, modified PPPASI, PPSI, and PGA for palms and soles) for that visit. See [Appendix E](#).

t Indicated assessments should be performed before any tests, procedures, or other consultations (PPPASI, modified PPPASI, PPSI, and PGA for palms and soles) for that visit. See [Appendix H](#), [Appendix I](#), respectively.

